The primary outcome is physician billing for ACP (data available directly from Sound Physician-submitted claims with a 1 quarter lag). The primary hypothesis (H1) is that hospital ACP billing practices after distribution of the video game will increase (more than would be expected by secular trends alone). A priori post-hoc hypotheses include: (H2) The larger the proportion of hospital physicians who play the game, the greater the increase in ACP rates, and (H3) Differences in hospital billing practices before-and-after distribution of the video game will be positively associated with the proportion of physicians who have completed their organization's ACP e-curriculum.

The secondary outcomes are episode-based patient healthcare use and mortality (data available from CMS with a 2-year lag).

3. Study Design

Note: All aspects of this study design will need to be re-appraised in light of the evolving Covid-19 pandemic and the associated secular disruptions in hospital medicine staffing, medical decision-making processes, and mortality among older adults.

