Employability. Study participation is not a condition of employment. Sound collects and reports multiple measures of hospitalist performance. These are conditions of employment. Hospitalists already receive data on their own ACP performance monthly, which is reported to their direct hospital supervisors in comparison with all of the hospital's other hospitalists' performance. There is no central Sound policy regarding how hospital supervisors use any

performance data, including ACP performance. This study will not change these reporting procedures. Therefore, responses should not influence employability. Indeed, if the intervention(s) are effective, participants randomized to active treatment will improve their performance. A theoretical concern is if increased attention to ACP crowded out hospitalists' focus on other quality targets. While this was not originally a secondary outcome proposed in the original protocol, the administrative and statistical feasibility of adding this safety measure will be assessed (see below).

Unconsented research participants (patients of hospitalists):

The three main risks to unconsented research participants (patients of participating hospitalists) are violation of rights due to non-consent and lack of voluntariness, breach of confidentiality, and shortened survival time associated with preference-concordant treatment associated with modifying code status to "do not resuscitate" or completing ACP documents such as physician orders for life-sustaining treatment (POLST) as well as potential medical undertreatment associated these orders.

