**Statistical Analysis Plan**

**Hopewell Hospitalist: A Video Game Intervention to Increase Advance Care Planning by Hospitalists [Efficacy Trial]**

**NCT 04557930**

**11 November 2021**

## Statistical Analysis Plan

### Variable Specification

Variable type	Variable Name		Variable Format	Notes
Primary Analysis				
dependent variable	primary	acpbilled	dichotomous (0/1)	
	secondary	mortality	dichotomous (0/1)	
		length of stay	continuous	
		7-day readmission	dichotomous (0/1)	
		30-day readmission	dichotomous (0/1)	
	ICU usage	dichotomous (0/1)		
primary predictor	phase of trial at hospital		categorical [0 = pre; 1 = enrollment and post]	We will retain 3-level coding until the point of the analysis (pre 0; enrollment 0.5; post 1)
time	date		categorical with days since start of baseline period as categorical labels	Will capture an anticipated non-linear and differential impact of COVID across time
	block		categorical	Further captures the COVID effect by adjusting for differential time-trends by block. Will allow for heterogeneity as these were pre-formed and control for the same general region of the country.
patient covariates	patient age		categorical variable (65-74, 75-84, 85+)	Association between age and probability of ACP billing is continuous with no inflections at specific ages (based on graphical analysis). We considered using the continuous variable but thought that the categorical variable provides more clinical context (e.g., an OR of 1.02 per year vs. OR 1.32 for patients age 74-85 and OR 1.76 for patients with age 85+)
	Charlson comorbidity index		categorical (0 to ≥5)	

	serious illness (selected based on differences in cohort between pre/post trial period)	dichotomous (0/1)	Serious illness codes based on Kelley et al. "Identifying older adults with serious illness" 2019 J Pain Symptom Management
	illness severity (evidence of organ failure)	exclude for endogeneity	It may be difficult to parse the differences between organ failure and receipt of LST (for example - codes for respiratory failure may be equivalent to the receipt of mechanical ventilation in some institutions). Since we anticipate that stepped-wedge design takes care of differences in cohort, we exclude these codes.
	surprise question	dichotomous (0/1)	Include if available by the time we are ready to submit. Otherwise exclude for missingness.

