### Primary Analysis

Let  $Y_{ijt}$  denote the binary outcome variable (coded as 1 if an ACP conversation occurred and 0 otherwise) for patient  $i$  seen at hospital  $j$  at time  $t$ ,  $Game_{jt}$  a binary variable indicating whether hospital  $j$  has received the Game during period  $t$  ( $Game_{jt} = 1$  if received by hospital  $j$  before or during period  $t$  and 0 otherwise),  $x_{ijt}$  a vector of patient-level covariates,  $z_j$  a vector of hospital-level covariates and  $\theta_j$  a random effect for hospital. The mathematical specification of the statistical model is given as  $Y_{ijt} | \theta_i \sim Bernoulli(\pi_{ijt})$ , where

$$\text{logit}(\pi_{ijt}) = \log \left( \frac{\pi_{ijt}}{1 - \pi_{ijt}} \right) = \beta_0 + \beta_1 t + \beta_2 Game_{jt} + \beta_3 x_{ijt} + \beta_4 z_j + \theta_j$$

where  $\theta_j \sim \text{Normal}(0, \tau^2)$  is the distribution of the hospital-level random effects to account for the fact that the statistical significance of inferences about the effect of the game are likely to be reduced by the clustering of patients in hospitals. The model includes fixed-effects for time-period,  $\beta_{1t}$ , to allow for an unstructured trend across calendar time, which makes the effect of the game (the primary target of inference) to be estimated net of any time-trend. The key coefficient of interest is  $\beta_2$ , which captures the structural shift in the outcome of patients who were enrolled in the study when the hospital receives the iPads, net of general trends across time and other covariates. Because this is a cluster-randomized study, there is a risk that the hospitals in each step are not perfectly balanced, despite attempts to balance these during randomization by forming blocks, and that the distributions of patient characteristics of patients treated by a given hospital may vary across time. To mitigate these concerns, we will adjust for judiciously selected patient and hospital covariates that we hypothesize are reasonably likely to be associated with the outcome. We do not plan to adjust for time-varying hospital-level covariates but we will adjust for whether the hospital was in other programs (e.g., the bundled payment care initiative (BPCI) program) that might influence the culture of the hospital towards ACP; an advantage of adjusting for BPCI participation is that we may obtain more precise inferences.

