#### *Power calculation*

We arrived at our sample size using a combination of feasibility (cost) and assumptions regarding effect size, absent any pilot data about the latter. For each step, we plan to recruit between 25 to 30 physicians from each of 4 to 8 hospitals. Assuming a baseline ACP rate of 22% (rising by 1.5 percentage-points per-quarter), a hospital intra-class correlation (ICC) coefficient of 0.01-0.10, and 160 evaluable patients per physician-quarter, we can detect a 3.5

percentage-point difference between ACP practices before and after the distribution of the intervention using a two-sided test at the 0.05-level with power in excess of 99%, even under the most conservative sample-size assumptions. If we invert the problem to find the smallest effect-size at which our study has 80% power, we find that in the most conservative scenario (76,800 total patients) we can detect a 1.5 percentage-point difference and in the most optimistic scenario (192,000 total patients), we can detect a 1 percentage-point increase.

The method of computing power for this stepped-wedge design follows the commonly used strategy for cluster randomized trials of first determining the design-effect, which can be thought of as a measure of the inefficiency of the given design in comparison to a completely randomized design that is expressed in terms of a ratio of the sample-sizes needed to obtain equally precise estimates, and then applying conventional power calculations. The latter computes power for a two-population comparison using the effective-sample-sizes determined from the design-effect. We estimate the design-effect using the expression in Woertman et al (2013), that was clarified and illustrated in Hemming (2016). Because hospitals may induce correlations in the outcomes of patients who receive care from them, we perform illustrative power calculations that account for the net impact of clustering at the hospital-level. Based on our own prior research and published results of others, we decided that the ICC of hospital is highly likely to be in the range 0.01 to 0.10. The design-effects across the optimistic and pessimistic scenarios ranged between 2.88 and 3.14, implying that for all considered scenarios the stepped-wedge design is about 33% as efficient as a patient-level completely randomized design. The effective sample-sizes (ESS) per group ranged from 30,603 to 12,388 patients per group over the study period (the 5 steps and a baseline period).

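### Readmission and length of stay are separate secondary outcomes with no method for death as a competing event, although the protocol names shortened survival as a patient risk

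*SAP*

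**What the plan says.** Protocol Section 2 states: "The secondary outcomes are episode-based patient healthcare use and mortality". It gives no hypothesis or direction for these outcomes; H1 to H3 all concern ACP.

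The SAP's Variable Specification table turns this into five secondary dependent variables: mortality, "length of stay", "7-day readmission", "30-day readmission" and ICU usage. Length of stay is continuous and the others are 0/1. The notes column is empty for all of them. The SAP gives no denominator for readmission (all admissions or live discharges), no time window for mortality and no rule for a stay that ends in death. It also has no composite, competing-risk or survivor analysis. The only model written out, under Primary Analysis, is for ACP: its outcome is said to "denote the binary outcome variable (coded as 1 if an ACP conversation occurred and 0 otherwise".

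Protocol Section 6a, on the patients of participating hospitalists, lists "shortened survival time associated with preference-concordant treatment associated with modifying code status" to do-not-resuscitate, or with completing ACP documents, among three main risks, together with potential medical undertreatment. No size is given.

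**The concern.** Death before day 7 or day 30 precludes a later readmission in that window, and death in hospital ends the stay. When an intervention cannot plausibly affect death, this blurs utilisation outcomes equally before and after crossover. Here the protocol itself raises the possibility that the intervention affects survival, so the competing event may differ between the two conditions.

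Two consequences follow. If deaths before readmission become more frequent while the tendency to be readmitted among those alive is unchanged, the readmission proportion falls. If in-hospital deaths change, mean stay changes for reasons unrelated to efficiency of care. A separate mortality result shows that something happened, but it does not correct the readmission or stay estimate.

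Restricting readmission to live discharges would not solve the problem. Deaths after discharge would still preclude readmission, and the restriction conditions on surviving to discharge, which the intervention may affect.

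At stake is how the utilisation results are interpreted. A lower readmission rate is easily read as a gain, and any real downstream effect would pass through the same modest shift in ACP as the artefact.

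**Working it through.** **The plan's own figures.** The SAP's power figures concern ACP only, but their effective sample sizes (ESS) help to judge detectability. With 5 steps, one baseline period and n patients per hospital-period, the stepped-wedge design effect that the SAP cites is

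DE = 6 × [1 + ρ(5n + n − 1)] / [1 + ρ(5n/2 + n − 1)] × 3(1 − ρ) / [2(5 − 1/5)], with ESS per group = (N/2)/DE.

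- N = 76,800, 30 hospitals, ρ = 0.01: n = 427, DE = 3.10, ESS = 12,388 (SAP: 12,388).
- N = 192,000, 40 hospitals, ρ = 0.01: n = 800, DE = 3.137, ESS = 30,604 (SAP: 30,603).
- Detectable ACP difference from 22% at 80% power: 1.49 and 0.95 points (SAP: 1.5 and 1).

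The SAP's figures reproduce.

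**Size of the readmission artefact.** The documents give no death or readmission rates, so these inputs are assumptions, apart from the ACP rise:

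- rise in ACP: 3.5 points (the difference used in the SAP's Power calculation);
- f: added deaths within 30 days per added ACP conversation, 0.05 to 0.20;
- g: share of those patients who would otherwise have been readmitted, 0.2 to 0.4;
- no true effect on readmission.

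Per 100 added conversations: 100 × f × g = 1 to 8 fewer readmissions.

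Across all patients:

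- Fall in readmission = 3.5 × f × g = 0.035 to 0.28 points.
- Rise in mortality = 3.5 × f = 0.175 to 0.70 points.
- Rise in death-or-readmission = 3.5 × f × (1 − g) = 3.5 × 0.05 × 0.6 to 3.5 × 0.20 × 0.8 = 0.105 to 0.56 points.

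Readmission alone and the death-inclusive outcome therefore move in opposite directions.

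**Would it be noticed?** This is a two-sided 0.05 test of two proportions at the SAP's ESS, assuming that ESS carries over to these outcomes. Assumed baselines are 20% readmission and 5 to 10% death.

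| Change | ESS 12,388 | ESS 30,603 |
|---|---|---|
| Readmission −0.28 points | 9% | 14% |
| Readmission −0.035 points | 5% | 5% |
| Mortality +0.70 points | 44–69% | 81–97% |
| Mortality +0.175 points | 7–10% | 11–17% |

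The smallest mortality rise detectable at 80% power is about 0.5 to 1.1 points over these baselines and ESS values.

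**A wider scenario, to check direction.** Take constant hazards over 30 days, with readmission r and death without readmission d at baseline. The total cumulative hazard is −ln(1 − r − d), split in the ratio r : d; multiply the death part only. With r = 15%, d = 5% and a 1.25-fold death hazard, readmission falls by 0.10 points and death-or-readmission rises by 1.1. With r = 20%, d = 10% and a doubled hazard, the figures are 1.08 and 7.9. The direction is confirmed, but the size is not credible here: a 1.1-point rise already needs 1.1/0.035 ≈ 31 extra events per 100 added conversations, above the 5 to 20 assumed.

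**Length of stay.** With constant hazards, baseline mean stay L and in-hospital death m, multiplying the death hazard by k gives mean stay L/[1 + m(k − 1)].

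- L = 5, m = 0.03, k = 1.5: 5/1.015 = 4.93 days (−0.07).
- L = 6, m = 0.05, k = 2: 6/1.05 = 5.71 days (−0.29).

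These cases raise in-hospital death by 1.4 points (3% to 4.43%) and 4.5 points (5% to 9.52%), so they too exceed what a 3.5-point ACP rise would produce under the assumptions above. The constant-hazard model also builds in a fall. If added deaths come later than discharge would have, mean stay rises.

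**The case against.** The strongest reply is that the SAP is silent and does not prescribe a faulty analysis, that mortality is itself a secondary outcome, and that the artefact is too small to mislead. Much of this stands.

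- A reader might infer that patients who die are to be coded as not readmitted. The SAP does not say so; it gives variable names and formats only. The supportable statement is that it has no method for death.
- A reader might infer that the protocol expects ACP to shorten survival. It lists this as a risk, ties it to preference-concordant treatment, and argues in the same section that ACP is minimal risk.
- A reader might infer that a false benefit is likely. Under the assumed inputs, even the largest artefact reaches significance only 9 to 14% of the time, and mortality moves 2.5 to 5 times as far (1/g).
- The documents nowhere call lower readmission or shorter stay favourable, and the direction for length of stay is not fixed.
- Readmission among all admissions, read beside mortality, is a legitimate total-effect quantity. Replacing it with a composite would score a preference-concordant death as a failure, which is debatable in an ACP trial.

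What does not stand is the claim that separate reporting is enough. Mortality has no stated window, so deaths after discharge may or may not be counted. Much of the assumed range of excess mortality (0.175 to 0.70 points) lies below what the trial could reliably detect. A safety board's review does not change the readmission or stay estimates.

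**Conclusion.** The point holds as a worthwhile improvement to the secondary analyses. Death is a competing event for readmission and length of stay, the protocol names a route by which the intervention could change it, and the SAP provides no method for it.

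The readmission artefact is about 0.04 to 0.28 points if ACP rises by 3.5 points and the assumed inputs hold. Its direction is downward if deaths rise and the readmission hazard among the living is unchanged. For length of stay, neither the direction nor the size can be fixed from the documents. The artefact is small in absolute terms, but a true effect on readmission would be diluted through the same 3.5-point shift and could be no larger. The documents do not support a stronger conclusion that the planned results are biased or that a spurious benefit is likely. The primary outcome and its power are unaffected.

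**What to change.** Amend the SAP before the CMS outcome data, which the protocol expects with a 2-year lag, are analysed:

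1. Keep 7-day and 30-day readmission and state the denominator (all admissions or live discharges).
2. Beside each, add a death-inclusive analysis in the same window: death-or-readmission, or days alive and out of hospital to day 30 from admission. Show death and readmission as components.
3. Define mortality over a fixed window from admission, and read the utilisation results jointly with it.
4. Analyse length of stay as time to live discharge, with in-hospital death as a competing event.

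The cost is SAP wording, some re-coding of data already planned and a little more analysis. The composite mixes two events and counts a preference-concordant death as an event, so it should accompany the components and not replace them.

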### Primary Analysis

Let  $Y_{ijt}$  denote the binary outcome variable (coded as 1 if an ACP conversation occurred and 0 otherwise) for patient  $i$  seen at hospital  $j$  at time  $t$ ,  $Game_{jt}$  a binary variable indicating whether hospital  $j$  has received the Game during period  $t$  ( $Game_{jt} = 1$  if received by hospital  $j$  before or during period  $t$  and 0 otherwise),  $x_{ijt}$  a vector of patient-level covariates,  $z_j$  a vector of hospital-level covariates and  $\theta_j$  a random effect for hospital. The mathematical specification of the statistical model is given as  $Y_{ijt} | \theta_i \sim Bernoulli(\pi_{ijt})$ , where

$$\text{logit}(\pi_{ijt}) = \log \left( \frac{\pi_{ijt}}{1 - \pi_{ijt}} \right) = \beta_0 + \beta_1 t + \beta_2 Game_{jt} + \beta_3 x_{ijt} + \beta_4 z_j + \theta_j$$

where  $\theta_j \sim \text{Normal}(0, \tau^2)$  is the distribution of the hospital-level random effects to account for the fact that the statistical significance of inferences about the effect of the game are likely to be reduced by the clustering of patients in hospitals. The model includes fixed-effects for time-period,  $\beta_{1t}$ , to allow for an unstructured trend across calendar time, which makes the effect of the game (the primary target of inference) to be estimated net of any time-trend. The key coefficient of interest is  $\beta_2$ , which captures the structural shift in the outcome of patients who were enrolled in the study when the hospital receives the iPads, net of general trends across time and other covariates. Because this is a cluster-randomized study, there is a risk that the hospitals in each step are not perfectly balanced, despite attempts to balance these during randomization by forming blocks, and that the distributions of patient characteristics of patients treated by a given hospital may vary across time. To mitigate these concerns, we will adjust for judiciously selected patient and hospital covariates that we hypothesize are reasonably likely to be associated with the outcome. We do not plan to adjust for time-varying hospital-level covariates but we will adjust for whether the hospital was in other programs (e.g., the bundled payment care initiative (BPCI) program) that might influence the culture of the hospital towards ACP; an advantage of adjusting for BPCI participation is that we may obtain more precise inferences.

The reason why physician is excluded from the above model is that a patient may receive care from multiple physicians during their hospital stay. This makes it difficult to designate a single physician as being responsible for the patient's care and thus whether or not they receive an ACP conversation. In our primary analysis we hold the hospital as a collective unit as being responsible for the patient and, therefore, exclude any involvement of physician factors or identifiers in relation to the likelihood of the patient having an ACP conversation. However, based on analyses of preliminary data, we anticipate that for 80% of hospitalizations a single physician will dominate the care of the patient. Therefore, in a sensitivity analysis, we will

add a physician layer to the above model and perform a physician-level analysis. Where more than one physician treats a patient, we will assign the patient to the discharging physician, as per the practice of the staffing organization. The resulting statistical model will be a three-level model with physician as the second level (between patient and hospital) to allow patients to be nested within physicians that are in turn nested within hospitals. Because patients are not randomized to physician, we will consider adjusting for physician covariates, emulating some of the secondary analyses described below.

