	COVID status	dichotomous (0/1)	Based on the presence of an ICD10 diagnosis code or a flag created by the treating physician that the patient was confirmed positive.
hospital covariates	risk-adjusted ACP rate prior to the start of the trial.	continuous	The correlation between risk-adjusted ACP rate and change in ACP rate is 0.23 (and therefore the risk of collinearity is small); these variables capture distinct effects.
	change in ACP rate between Quarter 2 2019 and Quarter 1 2020	continuous	
	practice size	quartiles	
	region	categorical	
	COVID admissions – fraction of total admissions with COVID in the month of the date of admission	continuous	
	COVID prevalence - HRR-level COVID rate in the month of the date of admission	continuous	We will test for collinearity with COVID admissions and exclude based on the variance inflation factor
random effect	hospital	categorical	
Secondary Analysis (Mediation)			
mediator	completion	dichotomous (0/1)	Whether physician finished the Game
	adherence (minutes)	quartiles	Minutes playing the Game

	engagement	quartiles	Physician experience with the game as captured by the Narrative Engagement Scale (scored out of 20)
	change in attitudes	difference in median attitude score before and after exposure	We control for baseline score to separate level effects from change- variable effects
random effect	physician, hospital	categorical	
Secondary Analysis (moderation)			
moderator (hospital and physician- level)	contextual effect – site cooperation rate	continuous	consider as covariate and interaction with MD adherence; remove interaction-effect if not-significant at the 0.05-level
	opportunity – proportion of physicians seen by patient who enrolled in the trial.	continuous	The total number of physicians will be considered as an alternative specification. One additional analysis will be a repeated measures model at the patient level where we define a separate outcome for each physician encountered by the patient until an ACP conversation occurred.
	physician CME compliance	dichotomous	

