The second part of the calculation is to determine the power of a two-group comparison of a binary outcome in the absence of clustering when the total sample-size per group equals the above values for the ESS. Because the sample-sizes are still reasonably large, an

asymptotic normal approximation is well justified, especially at a baseline ACP rate of 22%. Because we generally err on the side of making conservative estimates about the level of information available (e.g., we may extend the baseline period in which can retrospectively acquire data to 3-months). Therefore, this approximate two-step calculation yields trustworthy estimates of power that, if anything, are expected to err on the side of being conservative.

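### The primary model's only random effect is a hospital intercept fixed over time, so hospital-specific drift is left out of the standard error of the game effect

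*SAP*

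**What the plan says.** The equation in SAP, Primary Analysis contains a single random effect, theta_j, indexed by hospital only. The SAP explains that Normal(0, tau^2) "is the distribution of the hospital-level random effects to account for the fact that" clustering of patients is likely to weaken inference about the game. The random-effect row for the primary analysis in SAP, Variable Specification likewise lists only hospital. The sensitivity model adds a physician level, also constant in time.

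Time is handled by fixed effects. The date term "Will capture an anticipated non-linear and differential impact of COVID across time", and the block row allows trends to differ between blocks of hospitals. On hospital covariates that change over time, the SAP says two different things:

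- Variable Specification lists COVID admissions, defined as the "fraction of total admissions with COVID in the month of the date of admission", and a monthly COVID rate for the hospital referral region (HRR).
- Primary Analysis states: "We do not plan to adjust for time-varying hospital-level covariates".

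SAP, Power calculation uses one ICC per scenario, in the range 0.01 to 0.10. It reports that "The design-effects across the optimistic and pessimistic scenarios ranged between 2.88 and 3.14", and concludes that "this approximate two-step calculation yields trustworthy estimates of power that, if anything, are expected to err on the side of being conservative".

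**The concern.** Date effects remove drift shared by all hospitals, and block trends remove drift shared within a block. Neither removes the drift of one hospital relative to its block. With only a constant intercept, the model treats that drift as independent patient-level noise and averages it over hundreds of patients per hospital-period. The model-based standard error of beta_2 is then too small.

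The documents give reason to expect such drift. Protocol, Study Design asks for the design to be re-appraised because of "secular disruptions in hospital medicine staffing, medical decision-making processes, and mortality among older adults". The SAP adjusts for each hospital's "change in ACP rate between Quarter 2 2019 and Quarter 1 2020", which treats hospitals as having different trajectories. The COVID terms could absorb part of the drift if they are in the model, but they would not absorb drift from staffing or local practice unrelated to COVID.

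At stake are the width of the primary confidence interval, the size of the 5% test, and the stated power. The planned model has no term that would reveal the problem.

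**Working it through.** **Inputs.** From SAP, Power calculation: ACP rate 22%, ICC 0.01 to 0.10, 5 steps plus a baseline (6 periods), 4 to 8 hospitals per step (20 to 40 in all), 76,800 or 192,000 patients, effective sample sizes of 12,388 and 30,603 per group, and detectable differences of 1.5 points and 1 point. The CAC is the correlation between a hospital's underlying rates in two different periods. It is not in the documents and is varied below as an assumption.

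**1. Reproducing the SAP's figures.** With k = 5 steps, one baseline period, one measurement per step and n patients per hospital-period, the stepped-wedge design effect with a time-constant ICC is

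DE = 6 × [1 + ICC(6n − 1)] / [1 + ICC(3.5n − 1)] × 3(1 − ICC) / [2(5 − 1/5)].

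- 30 hospitals, n = 76,800/(30 × 6) = 426.7, ICC 0.01: 6 × 26.59/15.92 × 0.3094 = 3.10; 38,400/3.10 gives 12,388.
- 40 hospitals, n = 800, ICC 0.01: 6 × 48.99/28.99 × 0.3094 = 3.14; 96,000/3.137 gives 30,604.
- 20 hospitals, n = 640, ICC 0.01: DE 3.126, giving 12,284 (0.8% below the stated 12,388).
- ICC 0.10 gives a DE of about 2.89 in all three layouts.

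The formula has no term for correlation that changes between periods, so the SAP's figures assume CAC = 1.

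**2. True size of the planned test.** Let v = 0.22 × 0.78 = 0.1716. A hospital-period mean has intercept variance ICC·CAC·v, hospital-by-period variance ICC(1 − CAC)v, and patient variance (1 − ICC)v/n. Linear GLS on these means compares the random-intercept estimator's true (sandwich) SE with its model-based SE. The ratio is close to √[1 + n·ICC(1 − CAC)/(1 − ICC)], and the true size is 2Φ(−1.96/ratio).

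Example, 30 hospitals, ICC 0.05, CAC 0.90: the drift variance is 0.05 × 0.10 × 0.1716 = 0.000858 (an SD of 2.9 points), and the patient variance is 0.95 × 0.1716/426.7 = 0.000382. The ratio is √(1 + 2.25) = 1.80 and the size is 27.6%.

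True size (%) of the nominal 5% test at ICC 0.01 / 0.05 / 0.10:

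| Layout | CAC 1 | 0.99 | 0.95 | 0.90 |
|---|---|---|---|---|
| 30 × 427 | 5 / 5 / 5 | 5.5 / 7.6 / 10.6 | 7.5 / 17.8 / 28.5 | 10.0 / 27.6 / 41.3 |
| 20 × 640 | 5 / 5 / 5 | 5.7 / 9.0 / 13.4 | 8.8 / 23.1 / 35.8 | 12.5 / 34.8 / 49.1 |
| 40 × 800 | 5 / 5 / 5 | 5.9 / 10.0 / 15.4 | 9.7 / 26.6 / 40.1 | 14.4 / 39.0 / 53.3 |

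If covariates absorbed 50% or 75% of the drift variance (also an assumption), the 30 × 427 figures at CAC 0.90 would fall from 27.6% to 17.8% or 11.6% at ICC 0.05, and from 10.0% to 7.5% or 6.2% at ICC 0.01.

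**3. Check with a logistic random-intercept model.** This used a Laplace fit, 30 × 427 × 6, 2,000 replicates and no game effect, with the ICC on the proportion scale. It does not carry the SAP's full covariate list.

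| ICC / CAC | Planned model | With hospital-by-period term |
|---|---|---|
| 0.01 / 1 | 4.8% | 4.5% |
| 0.01 / 0.90 | 10.2% | 6.2% |
| 0.05 / 0.99 | 8.6% | 6.1% |
| 0.05 / 0.90 | 27.8% | 5.3% |
| 0.05 / 0.90, 75% absorbed | 11.8% | 5.5% |
| 0.10 / 0.90 | 42.7% | 5.2% |

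With the ICC defined on the logit scale the rates are lower: 8.0% against 5.9% (0.01 / 0.90) and 20.6% against 6.4% (0.05 / 0.90).

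**4. Detectable difference and power, allowing for the drift.** Detectable difference at 80% power = (1.96 + 0.84) × SE from the model that includes the hospital-by-period effect, in points, at ICC 0.01 / 0.05 / 0.10:

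- 76,800 patients, 30 hospitals (SAP: 1.5): 1.5 / 1.6 / 1.7 at CAC 0.99; 1.6 / 2.1 / 2.6 at 0.95; 1.75 / 2.6 / 3.4 at 0.90.
- 76,800 patients, 20 hospitals: 1.9 / 3.0 / 4.0 at CAC 0.90.
- 192,000 patients, 40 hospitals (SAP: 1): 1.25 / 2.1 / 2.8 at CAC 0.90.

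Power at 3.5 points, CAC 0.90, 76,800 patients: above 99% / 96% / 83% with 30 hospitals, and above 99% / 90% / 68% with 20.

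**The case against.** The harm is conditional. The documents give no CAC, at CAC 1 nothing changes, and at ICC 0.01 with CAC 0.99 the effect is trivial. The SAP postdates the protocol's warning about disruption, and its date, block and COVID terms can be read as the response to it; patient covariates may also absorb case-mix drift. The ICC range in the SAP is a planning range, not shown to be residual after adjustment, so the largest sizes above may overstate the case. The physician-level sensitivity model could pick up drift caused by changing physician mix.

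Much of this stands as a reason to read the figures as a range. It does not remove the gap. None of the fixed terms gives a variance to drift of one hospital within its block. The monthly COVID terms cannot be relied on while the SAP contradicts itself about them, and with 75% of the drift absorbed the size at ICC 0.05 and CAC 0.90 is still about 12%. The physician model is only a sensitivity analysis and does not capture change within physicians. The layout is inferred from the SAP, but the smallest layout it allows, 20 hospitals, gives worse results than 30.

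**Conclusion.** The concern holds. The SAP's standard error, its 1.5-point and 1-point detectable differences and its power above 99% are right for clustering only if the within-hospital correlation is constant over time. Under the assumed CAC range of 0.90 to 0.99, the true size for 30 hospitals runs from 5.5% to 41.3% across the SAP's ICC range. The trial keeps at least 83% power for 3.5 points with 30 hospitals in these cases, but this falls to 68% with 20 hospitals at ICC 0.10 and CAC 0.90. The SAP supports its claim of conservatism by caution about how much data will be available, and that reason does not cover a CAC below 1. The missing term is certain from the text. How much it matters depends on the unknown CAC, on the ICC and on how much drift the covariates remove. This should be fixed before analysis.

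**What to change.** 1. Add a hospital-by-period random effect to the primary equation: logit(pi_ijt) = ... + theta_j + u_jm, with u_jm ~ Normal(0, gamma^2) for hospital j in period m. Fix the unit of m in advance; month is natural, because the COVID terms are monthly. Test beta_2 from this model.
2. Pre-specify a permutation test over the randomised step order, within the randomisation strata, as a check. It is useful because the extended model still rejected at about 6% in some simulated cases.
3. Reconcile Variable Specification with Primary Analysis on whether the monthly COVID covariates are in the primary model.
4. Estimate the CAC from the pre-trial hospital ACP rates already in use (Quarter 2 2019 to Quarter 1 2020). These are quarterly and largely pre-pandemic, so also restate power and detectable difference over a CAC of about 0.8 to 1.
5. Remove or qualify the statement that the power calculation errs on the conservative side.

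The cost is SAP wording and one variance component in the same software. In simulation without drift at ICC 0.01, the added term widened the SE by about 2% (0.0306 against 0.0301 on the logit scale). If drift is real, the interval will be wider and the stated power less favourable.
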